## 9.7. STUDY DRUG COMPLIANCE

Summary statistics for compliance to study drug will be presented using descriptive statistics based on the SAF overall and by Pre-randomization Group or randomized treatment group, as appropriate, across all study periods and by study period. Compliance will also be summarized by category (<75%, 75-125% and >125%). A listing of compliance will also be presented.

### 9.7.1. DERIVATIONS

Compliance will be calculated as the volume of solution taken during a study period (i.e., total dispensed – total returned) divided by the volume of solution that should have been taken by the subject during that study period, expressed as a percentage i.e.

$$\text{Compliance (\%)} = \frac{\text{Volume of solution taken during a study period}}{\text{Volume of solution that should have been taken during the study period}} \times 100\%$$

where:

- Volume of solution taken is defined as follows:  
     Volume of solution dispensed at the end of the previous study period – volume solution returned at the end of the current study period
- Volume of solution that should have been taken during a study period is defined as follows:  
     {Duration of treatment during the study period i.e., [(Date of the last dose during the Study Period – Date of the first dose during the Study Period) + 1] x volume of study drug corresponding to subject’s assigned dose during the period (refer to Table 6)}

Missing data will not be imputed for bottles that are not returned.

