6.7 Study Drug Dosing Diary

Subjects will complete the Study Drug Dosing Diary (Appendix 3) each morning from the start of the Open-label Titration Period until the end of the Double-Blind Randomized-Withdrawal Period. A Study Drug Dosing Diary will not be completed in the Open-Label Extension.

Subjects must have completed the Study Drug Dosing Diary on at least 10 out of the 14 days during the Stable-Dose Period occurring prior to the start of the Double-Blind Randomized-Withdrawal Period and must have indicated that they were compliant with dosing on at least 10 of the 14 days, or they will be discontinued from the study. The study staff will review the diary at each study visit and discuss it with the subject at each phone contact.

Confidential Page 53 of 148

Jazz Pharmaceuticals Clinical Trial Protocol: 15-006 Amendment 5

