### 9.6.1. DERIVATIONS

Duration of exposure to study drug, in days, will be computed as follows:

(Date of last dose of study drug administered during the study period – date of first dose of study drug administered during the study period) + 1.

For rollover subjects (i.e., subjects who rolled over into the OLE directly after completion of the DB RWP), the duration of exposure to study drug across all study periods, in days, will be computed as follows:

(Date of last dose of study drug administered during the study – date of first dose of study drug administered during the OTTP) + 1.

For OLE re-entry subjects, the duration of exposure to study drug across all study periods, in days, will be computed as follows:

[(Date of last dose of study drug administered during the Main Study – date of first dose of study drug administered during the OTTP) + 1] + [(Date of last dose of study drug administered during the OLE – date of first dose of study drug administered during OLE) + 1].

Time to get to the stable dose, in days, will be computed as follows:

(The Study Drug Administration Date of the Total Nightly Stable Dose when it was first achieved based on total dose consideration – date of the first day of the first Open-Label study drug dispensation) + 1. The stable dose determination and time to get to the stable dose will only be calculated for subjects entering the OL SDP.

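### SAP 9.7.1 ends the expected dosing volume at the subject's own last dose, so nights missed after it, while the subject is still in the period, cannot lower reported compliance

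*SAP*

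**What the plan says.** SAP 9.7.1 describes compliance as the volume of solution taken in a study period "divided by the volume of solution that should have been taken by the subject during that study period". Two definitions follow.

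- **Numerator:** "Volume of solution dispensed at the end of the previous study period – volume solution returned at the end of the current study period". It does not depend on any dose date. For bottles not brought back, the rule is "Missing data will not be imputed for bottles that are not returned".
- **Denominator:** the nightly volume for the assigned dose, multiplied by a number of days given as "Date of the last dose during the Study Period – Date of the first dose during the Study Period) + 1".

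SAP 9.6.1 uses the same span for duration of exposure, where its end is the "Date of last dose of study drug administered during the study period".

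SAP 9.7 summarizes the percentage on the Safety Population, overall and by Pre-randomization Group or randomized arm as appropriate, across all periods and by period. It also uses three categories: below 75%, 75 to 125%, and above 125%. A listing is planned too.

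Entry to the double-blind period uses a separate diary rule. Under Protocol 6.7 subjects "must have indicated that they were compliant with dosing on at least 10 of the 14 days" of the Stable-Dose Period.

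**The concern.** The denominator is introduced as what was due over the period and then computed from what the subject chose to do. Once a subject takes a last dose, the nights between it and the closing visit drop out of both numerator and denominator. Only missed, reduced or excess dosing between the first and last dose can move the ratio.

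This matters for reading the table. The primary endpoint uses diary days up to the date of Visit 16 (SAP 6.3, Table 1), so days off drug after the last dose enter the efficacy result. The double-blind compliance summary leaves out exactly those nights. A JZP-258 subject who stops taking drug mid-period but attends Visit 16 could appear fully compliant. In the Stable-Dose Period, the diary rule allows up to 4 of 14 nights without compliant dosing; if those are the last four, compliance can again read 100%. SAP 9.8.1.5 describes the enriched population as compliant with treatment, and this summary is a natural place to check that description.

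**Working it through.** The documents state no compliance figure, so there is none to reproduce. The cases below are hypothetical and apply the SAP formula as written.

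**Inputs**
- Period length: 2 weeks = 14 nights, for both the Stable-Dose and the double-blind period (SAP 3.1.1).
- Nightly volume: 18 mL at 9 g (SAP Table 3), which agrees with 9 g / 0.5 g/mL. With a constant assigned dose this cancels, so the percentages are the same at 9 mL.
- Last dose is read as the last dose actually taken, as in SAP 9.6.1.
- The subject stays until the closing visit with no recorded discontinuation, and all bottles are returned.

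**Formulas**
- SAP 9.7.1: volume taken / [(last-dose day − first-dose day + 1) × 18 mL].
- Over the period: volume taken / (14 × 18 mL) = volume taken / 252 mL.

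**Full dose every night, then stop**

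| Last dosed night | Taken (mL) | SAP 9.7.1 | Over 14 nights |
|---|---|---|---|
| 3 | 54 | 54/54 = 100% | 54/252 = 21.4% |
| 5 | 90 | 90/90 = 100% | 90/252 = 35.7% |
| 7 | 126 | 126/126 = 100% | 126/252 = 50.0% |
| 10 | 180 | 180/180 = 100% | 180/252 = 71.4% |
| 11 | 198 | 198/198 = 100% | 198/252 = 78.6% |

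The 75% cut falls at 0.75 × 14 = 10.5 nights. A full-dose subject who stops after night 10 or sooner is therefore reported in the 75-125% category although the figure over the period is below 75%.

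**Incomplete or excess dosing before the stop**

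| Pattern | SAP 9.7.1 | Over 14 nights |
|---|---|---|
| 80% of volume, nights 1-7 | 100.8/126 = 80% | 100.8/252 = 40% |
| 50% of volume, nights 1-7 | 63/126 = 50% | 63/252 = 25% |
| Full dose on nights 1-4, 6, 8 and 10 only | 126/180 = 70% | 126/252 = 50% |
| 130% of volume, nights 1-7 | 163.8/126 = 130% | 163.8/252 = 65% |

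Early stopping leaves the SAP figure at whatever it was up to the last dose. It reads 100% only when the volume taken by then equals the volume due by then.

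**One further dose**

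A subject with full doses on nights 1-7 reads 100%. If the same subject also doses on night 14, the span becomes 14 nights and the result is 144/252 = 57.1%. Taking one more dose lowers reported compliance from 100% to 57.1%, because the missed nights have become interior.

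**Open-Label Extension**

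On the same assumptions, a constant dose over 24 × 7 = 168 nights that stops after night 84 gives 84/84 = 100% by the SAP, against 84/168 = 50% over the period.

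**The case against.** The SAP spells out its denominator as duration of treatment, so it can be read as a deliberate measure of compliance while on treatment. For a subject withdrawn from study drug at the last dose, that is defensible. This stands, and the remedy should leave those subjects alone.

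Three stronger readings are tempting, and the documents do not support them.

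- **Everyone who stops early is reported as 100% compliant.** They are not. Missed, reduced or excess doses up to the last dose still count, as the 80%, 50%, 70% and 130% cases show.
- **Early stopping is hidden.** It is not. SAP 9.6 summarizes duration of exposure by period, by received treatment in the double-blind period, so a subject who doses for 7 nights shows 7 days there. The dosing diary is listed, and staff compare returned drug with it at Visits 15 and 16 (Protocol 7.1.4 and 7.1.5). The diary does not continue into the Open-Label Extension, but exposure duration does.
- **The efficacy result or baseline is biased by this formula.** Any dilution from subjects off drug occurs however the table is computed. The percentage is not in the ANCOVA (SAP 9.8.1.4) and is not named as a Per Protocol rule (SAP 5.6). Randomization uses the diary rule, so missed nights late in the Stable-Dose Period concern that rule; changing 9.7.1 would alter no baseline value.

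It can also be said that few subjects may be affected. SAP 9.8.1.5 reports that discontinuation of study drug in the double-blind period was rare in a similar Xyrem study. That bears on frequency, which stays unknown, and does not reconcile the formula with its own definition.

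**Conclusion.** The point holds in a limited form. SAP 9.7.1 defines the denominator as "the volume of solution that should have been taken by the subject during that study period" and then computes it only to the subject's own last dose. For subjects who remain in the period without a recorded discontinuation, missed nights after that dose cannot lower the reported figure. With complete dosing up to the stop, the overstatement is 28.6 percentage points for a stop after night 10 of 14 (100% against 71.4%) and 50 points for a stop after night 7. Stops at or before night 10 cross the SAP's own 75% cut.

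The conclusion assumes that last dose means last dose taken, that the assigned volume is constant, and that returned volumes are complete. It concerns a descriptive summary and listing only. It is still worth correcting: the table is planned by arm, the error runs in one direction for these subjects, and the dates needed are already collected.

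**What to change.** In SAP 9.7.1, define expected nights in two cases:

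- **Subject remains in the period:** date of the visit that closes it (Visit 14, 15, 16 or 33) minus the first-dose date. Dosing is at bedtime, so the night of the closing visit belongs to the next period. With the first dose on Day 1 and closure on Day 15, this gives 15 − 1 = 14 nights. Actual dates also absorb visit windows.
- **Discontinuation of study drug recorded before that visit:** keep last-dose date minus first-dose date plus 1. For a last dose on Day 7 this gives 7 − 1 + 1 = 7 nights. Plain subtraction would give 6 and report 7/6 = 117%.

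The second case must rest on a recorded discontinuation and not be inferred from the last dose, or the problem returns. A footnote should say that discontinued subjects are assessed only while on treatment. Leave duration of exposure in 9.6.1 as it is.

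The cost is one line of SAP wording and the matching programming, with no new data. Reported compliance may be slightly lower.

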5.1.1.2 Placebo

A matching oral solution to JZP-258 will be provided. The placebo formulation is an aqueous solution consisting of sodium citrate, malic acid and sucralose. All ingredients are compendial (USP/NF).

Placebo treatment is applicable to the Double-Blind Randomized-Withdrawal Period only.

Treatments Administered 5.1.1.3

During the Optimized Treatment and Titration Periods all subjects will receive open-label JZP-258.

Pre-randomization Groups 1 and 2

Subjects entering the study on Xyrem alone or on Xyrem plus an additional anticataplectic will be switched from their current dose of Xyrem to JZP-258 on a gram to gram straight conversion at the start of the Optimized Treatment and Titration Period and remain on that dose for 2 weeks. If further titration is needed, titration will proceed at a rate of 1 or 1.5 g per night per week during this period not to exceed a total dose of 9 g per night.

Pre-randomization Groups 3 and 4

Subjects entering the study receiving treatment with a non-Xyrem anticataplectic only or not treated with any anticataplectic agent will receive an initial dose of JZP-258 4.5 g per night at the start of the Optimized Treatment and Titration Period. Dose adjustments will proceed at a rate of 1 or 1.5 g per night per week until a tolerable dose of JZP-258 is reached over a period of 2 weeks. If needed, the dose of JZP-258 may be further titrated to a stable, tolerable, and effective dose that does not exceed a total dose of 9 g per night.

Pre-randomization Groups 2 and 3 will taper anticataplectics as described in Section 3.1.

During the Stable-Dose Period subjects will receive open-label JZP-258 at the same unchanged dose that they received during the last 2 weeks of the Optimized Treatment and Titration Period.

> Confidential Page 45 of 148

All subjects will receive blinded study drug during the Double-Blind Randomized-Withdrawal Period. At the end of the Stable-Dose Period, subjects enter the Double-Blind Randomized-Withdrawal and will be randomized 1:1 to receive either JZP-258 at the dose taken during the last 2 weeks of the Stable-Dose Period or JZP-258 placebo (at a volume equivalent to the JZP-258 dose taken in the last 2 weeks of the Stable-Dose Period).

Study drug will be dispensed at clinic visits and, if applicable, at intervals specified by state or local regulations or to resolve logistical issues.

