**Table 3 Total Daily Volume of Solution (mL)**

Assigned or Stable Dose of Study Drug (g)	Volume of Solution (mL)
4.5	9
5.0	10
5.5	11
6.0	12
6.5	13
7.0	14
7.5	15
8.0	16
8.5	17
9.0	18

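### The SAP 9.7.1 compliance formula assumes one dose and one dispensing per period, so subjects who take every dose can be classed below 75% or above 125% when the dose changes in titration.

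*SAP*

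**What the plan says.** SAP 9.7 reports compliance "across all study periods and by study period", as summary statistics and in three categories: below 75%, 75 to 125%, and above 125%. The OTTP and the OLE are therefore included.

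SAP 9.7.1 defines compliance as volume taken over volume that should have been taken.

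- **Denominator.** Treatment duration in days, multiplied by the "volume of study drug corresponding to subject’s assigned dose during the period". The text points to a Table 6. The SAP's list of tables ends at Table 4, and the dose-to-volume table is Table 3, which allows for an assigned or a stable dose and gives one volume for each.
- **Numerator, first description.** "total dispensed – total returned".
- **Numerator, operative definition.** "Volume of solution dispensed at the end of the previous study period – volume solution returned at the end of the current study period".

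For the subjects not on Xyrem at entry, Protocol 5.1.1.3 starts at 4.5 g and says: "Dose adjustments will proceed at a rate of 1 or 1.5 g per night per week until a tolerable dose of JZP-258 is reached". Protocol 7.1.2.3 allows titration in either direction and bars changes after Week 10. Protocol 5.1.2.2 allows titration in the OLE. Under Protocol 6.11 and Appendix 1, drug is dispensed in the OTTP at Visits 2, 6 and 10, and again during the OLE at Visit 30.

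**The concern.** A compliance measure should return 100% for a subject who takes exactly what was prescribed. This one does so only if the dose is constant and every dispensing is counted.

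In the OTTP a changing dose is part of the design, yet the SAP does not say whether the assigned dose is the starting dose, the stable dose or something else. The programmer's choice can move the same subject from one non-compliant category to the other. If the stable dose is meant, SAP 9.6.1 determines it only for subjects who enter the Stable-Dose Period, so subjects who leave during titration have no denominator.

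The two numerator descriptions also give different answers whenever drug is dispensed more than once in a period. That problem is separate from dose changes and reaches constant-dose subjects too.

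At stake is whether the OTTP and OLE compliance tables describe dose-taking or merely the shape of the titration.

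**Working it through.** **Inputs.** Concentration 0.5 g/mL (SAP 3.3). OTTP of 12 weeks, or 84 nights (SAP 3.1.1). Steps of 1 or 1.5 g per night per week, with a 9 g ceiling (SAP 3.3). No change after Week 10 (Protocol 7.1.2.3).

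**The plan's own figures.** Dose / 0.5 reproduces all ten rows of Table 3, from 4.5 / 0.5 = 9 mL to 9.0 / 0.5 = 18 mL. The table is correct. The documents state no compliance percentage.

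**Formula as written, counting all drug taken.** Compliance = total mL taken / (84 × one daily volume). The denominators are 84 × 9 = 756 mL at 4.5 g, 84 × 12 = 1008 mL at 6 g, and 84 × 18 = 1512 mL at 9 g.

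Three illustrative schedules, each with every dose taken:

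| Schedule over 12 weeks | mL taken | Against stable dose | Against starting dose |
|---|---|---|---|
| A. 4.5, 6, 7.5 g for one week each, then 9 g for 9 weeks | (4.5 + 6 + 7.5 + 81) × 7 / 0.5 = 1386 | 1386/1512 = 91.7% | 1386/756 = 183.3% |
| B. 4.5 g for 7 weeks, 6 g, 7.5 g, then 9 g for 3 weeks | (31.5 + 6 + 7.5 + 27) × 7 / 0.5 = 1008 | 1008/1512 = 66.7% | 1008/756 = 133.3% |
| C. 9 g for 8 weeks, 7.5 g, then 6 g for 3 weeks | (72 + 7.5 + 18) × 7 / 0.5 = 1365 | 1365/1008 = 135.4% | 1365/1512 = 90.3% |

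B is below 75% on one reading and above 125% on the other. A and C are each misclassified on one reading only.

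**How general this is.** There are 84 ways to go from 4.5 to 9 g in three 1.5 g steps, each at the start of a different week from Week 2 to Week 10. Against the starting dose all 84 exceed 125% (range 133.3 to 183.3%). Against the stable dose 16 of the 84 fall below 75% (range 66.7 to 91.7%). These are counts of schedules, not of subjects.

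**Literal one-dispensing numerator.** Assume that the Visit 2 supply covers exactly Weeks 1 to 4 and that none is returned at Visit 14. A subject on a constant 7.5 g (15 mL) is credited with 28 × 15 = 420 mL against 84 × 15 = 1260 mL, or 33.3%.

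**OLE (24 weeks).** With weekly 1.5 g steps from 4.5 to 9 g and all drug counted, the weekly doses sum to 4.5 + 6 + 7.5 + 21 × 9 = 207. That is 207/216 = 95.8% against 9 g and 207/108 = 191.7% against 4.5 g.

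**After the fix.** With the dose in force as denominator and all dispensings and returns in the numerator, every schedule above gives 100%.

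**The case against.** The strongest reply is that the denominator is underspecified rather than wrong. If the assigned dose means the stable dose, prompt up-titration stays in the middle category, and only late changes cross a limit. That stands, and it is why both readings are shown. Schedule B also does not fit every group: it reaches 9 g only at the start of Week 10, while Protocol 3.1.1.2 gives Group 4 up to 8 weeks to titrate.

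The first numerator description already states the sensible rule, so nobody need assume that later dispensings would be dropped. That is fair. The fault is a contradiction to be resolved, not proof of how the programming will be done.

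A reader might infer more than the documents support:

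- **All titration-period figures are wrong.** Subjects whose dose never changes are unaffected once all dispensings are counted. Groups 1 and 2 titrate only if needed, and so do rollover subjects in the OLE.
- **The all-period categories are wrong.** This is largely not shown. If period volumes are summed (an assumption) and the final dose continues for the four weeks after titration, then in weekly gram units schedule B gives (72 + 36)/(108 + 36) = 75.0% against the stable dose, inside the middle category. Schedule C gives (97.5 + 24)/(72 + 24) = 126.6%, barely outside it.
- **The missing rows below 4.5 g in Table 3 cause errors.** Every row is dose / 0.5, so a missing row produces no wrong number.
- **Efficacy results are touched.** Entry to the double-blind period uses dosing-diary days (10 of 14, Protocol 6.7), the per-protocol definition in SAP 5.6 does not cite this percentage, and the primary analysis does not use it.

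**Conclusion.** The point holds for the OTTP and, where the dose is titrated, for the OLE. Followed as written, the operative formula gives wrong compliance percentages for some subjects who take every dose. The error runs in both directions, and its size depends on a choice that the SAP leaves open: 66.7 to 135.4% against the stable dose, or 90.3 to 183.3% against the starting dose, for the three OTTP schedules worked here. The one-dispensing definition is wrong for any period with more than one dispensing, whatever the dose.

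The Stable-Dose and double-blind periods are normally unaffected, because the dose is fixed and drug is normally dispensed once. The schedules are illustrative, and the share of real subjects affected cannot be derived from the documents. The consequence is confined to descriptive tables, so this is a minor correction. Label: wrong as written.

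**What to change.** In SAP 9.7.1:

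1. Define expected volume as the sum, over treatment days in the period, of the prescribed nightly dose in force divided by 0.5 g/mL.
2. Define volume taken as all drug dispensed for the period minus all drug returned from it, and delete the one-dispensing definition.
3. Name the source of the dated doses. In the Main Study the dosing diary and the exposure derivations in SAP 9.6 and 9.6.1 point to dated records. In the OLE no dosing diary is kept (Protocol 6.7), so use the prescribed dose by date and confirm that it is captured.
4. Correct the Table 6 reference to Table 3.

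The cost is SAP wording and a programming change. The one item to check is the dated prescribed dose in the OLE, which the documents do not describe.

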**Table 3 Total Daily Volume of Solution (mL)**

Assigned or Stable Dose of Study Drug (g)	Volume of Solution (mL)
4.5	9
5.0	10
5.5	11
6.0	12
6.5	13
7.0	14
7.5	15
8.0	16
8.5	17
9.0	18

## 9.8. EFFICACY OUTCOMES

All efficacy analyses will be performed with the EFF, unless otherwise indicated.

## 9.8.1. PRIMARY EFFICACY ENDPOINT

### 9.8.1.1. PRIMARY EFFICACY ENDPOINT & DERIVATION

The primary efficacy endpoint is the change in average weekly number of cataplexy attacks from the two weeks of the OL SDP to the two weeks of the DB RWP.

Subjects will complete a daily cataplexy frequency diary each night prior to bedtime to record the number of cataplexy attacks that they had that day beginning at Study Day 1 up to the end of the DB RWP visit. Daily cataplexy frequency diary will not be collected during OLE.

For subjects with at least one day of cataplexy attack data, the average weekly number of cataplexy attacks over each of the two weeks (see Table 1) of the OL SDP will be calculated as follows:

$$\frac{\text{Total number of cataplexy attacks within the OL SDP period}}{\text{Number of days with non-missing data within the OL SDP period}} \times 7 \text{ days}$$

Average weekly number of cataplexy attacks over each of the two weeks of the DB RWP will be calculated similarly. Additionally, average weekly number of cataplexy attacks by week for each study period (see Table 1) will also be calculated as follows:

$$\frac{\text{Total number of cataplexy attacks within a week}}{\text{Number of days with non-missing data within that week}} \times 7 \text{ days}$$

